Study Protocol w/ Statistical Analysis Plan

Last Updated 10/17/2022

IRB

1) Protocol Title

Optimizing After Visit Instructions in an Outpatient Academic Rheumatology Clinic: A Prospective Randomized Open Label Trial

2) Objectives

The aim of this study is to assess the quality of standardized after visit instructions (AVI) and patient teach back in an outpatient academic rheumatology clinic by measuring patient retention of disease management and overall patient satisfaction. We propose a prospective randomized open label trial to determine if the presence of optimized and standardized discharge processes lead to better comprehension and retention of a patient's management plan.

Primary outcome will be level of retention based on the Follow-up Telephone Protocol.

Secondary outcomes assessed will include level of patient satisfaction based on our Post visit Survey and after visit instructions meeting patients' health literacy levels measured from the REALM-A.

3) Background

Patient education is an essential aspect of administering high quality care. How well patients understand their diagnoses and implement their plan of care is based on a multitude of factors that can drastically impact disease outcomes.^{1,2} One of the key social determinants that affects a patients ability to comprehend and act on their medical conditions is health literacy (HL). The Center for Disease Control (CDC) defines two different types of HL in their updated Healthy People 2030 initiative. Personal HL is "the degree to which individuals have the ability to find, understand, and use information and services to inform health-related decisions and actions for themselves and others". Organizational HL is "the degree to which organizations equitably enable individuals to find, understand, and use information and services to inform health-related decisions and action for themselves and others". These new definitions of HL now acknowledge that organizations have a responsibility, from a public health perspective, to address HL and optimize their approach to varying levels of personal HL.³

In 2003 the National Assessment of Adult Literacy (NAAL) preformed a large-scale survey of both literacy and HL. It showed that 36% of adults had basic or below basic HL skills. Of the patients that had the lowest health literacy they tended to be older than 65 years old, hispanic or black, male, less than a high school education, and at or below the poverty line.⁴ Low HL has been linked to poor health outcomes including in rheumatic diseases such as rheumatoid arthritis (RA) and systemic lupus erythematosus (SLE).^{5,6} Various studies have been performed assessing literacy rates in rheumatology clinics utilizing the tool, the Rapid Estimate of Adult Literacy in Medicine (REALM). These studies have shown that a range of 10.3% to 19% of patients, within rheumatology clinics, have less than a 9th grade reading level.⁷⁻⁹ Various strategies have been implemented to address the need for improving patients understanding of their medical conditions and management. The American Medical Association and the National Institute of Health have recommended that medical information be written at a 6th grade level.¹⁰ However a recent study looking at the medical information sheets for common rheumatologic drugs from prominent rheumatology organizations in Canada, the UK, and Australia, consistently showed readability scores higher than the 9th

IRB

grade level.¹¹ The “teach-back” (TB) method, where patients repeat in their own words, instructions from the provider is a strategy used to bridge gaps in health literacy. In the emergency room setting TB has been shown to lead to less revisits and better retention of instructions.¹² Teach back communication in rheumatology clinics has been shown to improve overall medication compliance.¹³ In the emergency room setting studies have shown that simplified and standardized after visit instructions can help increase patients overall understanding of their ER visit.¹⁴

An initial retrospective study showed us that written AVI were an underutilized resource in the Rush University Medical Center Rheumatology Clinic (RUMCRC). This retrospective assessment also showed that patients with more medications, higher comorbidity, and learning preferences that favor written AVI, did not receive more AVI.

For this study we seek to implement various strategies in an academic outpatient rheumatology setting that will address gaps in health literacy. These will include simple, standardized discharge instruction and patient teach back. With these strategies implemented, we will assess patients' retention of knowledge and comprehension of medical instructions. We will also determine the feasibility of implementing these strategies in a rheumatology clinic in terms of time. Long-term studies will analyze how these interventions may have impacted various health related outcomes and patient reported outcomes.

4) Inclusion/Exclusion Criteria

Inclusion Criteria

- Age > 18 yo
- Patients seen in the RUMCRC

Exclusion Criteria

- Tele-medicine visits
- English is not the primary language. This is due to inability of all providers to provide custom AVI due to language limitations

5) Procedures Involved

There will be three cohorts in total: the control group, the standardized AVI only group, and the standardized AVI with teach back group. The control group will involve patients receiving the current standard discharge process at the RUMCRC. The standardized AVI only group will involve patients receiving written standardized AVI that the patients will take home. The standardized AVI with teach back group will include standardized written AVI with the patient repeating to the provider which changes, and future management had been agreed upon during the visit. The standardized AVI will include a text template that providers will use to write customized after visit instructions for the patient that will be in addition to the after-visit summary.

Providers will be taught the standardized discharge approach through in-person education modules and handouts. This education will encompass a 30 minute didactic going over the tenants of the standardized AVI, accessing standardized AVI templates on EMR, and how

IRB

to perform appropriate teach back with patients. No providers that are implementing the intervention will be a part of the research team.

Patients will be randomized before the office visit. Patients will not be told which group they are in unless they explicitly ask. Providers will be told which intervention group a patient is a part of. If a patient is in the control group the providers will not be informed as to not impact behavior. Because of the randomization we believe confounding variables will be distributed equally throughout the groups.

All patients included in the prospective study will complete an arthritis adapted REALM (REALM-A) form at the observed visit to evaluate their health literacy level. All patients included in the prospective study will also complete an immediate post appointment questionnaire (Post Visit Satisfaction Survey) that will allow them to provide feedback, rate visit satisfaction, and evaluate how after visit instructions were implemented during the visit.

Within 1-2 weeks after the patient's initial visit, a standardized phone call will be performed where patients will be asked specific questions pertaining to their visit in terms of diagnosis, medications, plan, and follow-up appointments. We will score whether their understanding of their disease and management corresponds with what was discussed at the prior visit. This will be performed for all groups. This score will be assessed as our primary outcome.

Baseline data points will be collected for patients in both cohorts including: Basic demographics, new patients versus follow-up visit, MD-HAQ scores, REALM-A score, rheumatologic diagnosis, medications, Charleson co-morbidity scores, barriers to learning, and patient preferences for learning.

After the study, AVI provided will be assessed using Flesch-Kincaid Readability Scores and Grade levels to see how they correspond to patients baseline literacy.

6) Data Management

Summary tables (descriptive statistics and/or frequency tables) will be provided for all variables. Continuous variables will be summarized with descriptive statistics (n, mean, standard deviation, range, and median). Ninety-five (95) percent confidence intervals may also be presented, as appropriate.

Frequency counts and average will be provided for categorical data.

Data will be coded when stored for analysis. Data that is obtained for this study will be coded when stored for analysis. This data will be held under password locked computers that can only be accessed by persons who have approval for access via the IRB. Those that have access to the coded data will require a key to interpret the data. All data will be deleted at the completion of the study.

7) Risks/Benefits

Given the nature of intervention there is little to no risk in terms of patient outcomes. This study will collect private, identifiable information about human subjects. The main risk is to

IRB

subjects' confidentiality should an individual outside of the study team access the study data.

Benefits of this study, particularly in the intervention cohort, would be the potential for improved patient comprehension and retention of various aspects of their health.

8) Resources Available

REDCAP will be utilized to store and analyze data. SPSS will be utilized to perform statistical analysis.

[name] a clinical research coordinator at the RUMC Division of Rheumatology will assist with the consent process and recruitment process.

9) Confidentiality

Data will be stored under password protection with coded data on laptops owned by [name]

Data will only be accessible by those that are directly involved with obtaining data

10) Consent Process

Patients will be contacted with permission from their primary providers prior to their scheduled visit to discuss their voluntary participation in the study. If they agree to participate informed consent will be completed over the telephone and documents will be reviewed and signed electronically. If this is not feasible, they will be instructed to arrive 30 minutes early to their appointment to perform an in person consent. During this period they will sign a corresponding consent form outlining the risks/benefits and procedures of this study.

References

1. Weiss, B. D., Hart, G., McGee, D. L., & D'Estelle, S. (1992). Health status of illiterate adults: relation between literacy and health status among persons with low literacy skills. *The Journal of the American Board of Family Practice*, 5(3), 257–264.
2. DeWalt, D. A., Berkman, N. D., Sheridan, S., Lohr, K. N., & Pignone, M. P. (2004). Literacy and health outcomes: A systematic review of the literature. *Journal of General Internal Medicine : JGIM*, 19(12), 1228–1239. <https://doi.org/10.1111/j.1525-1497.2004.40153.x>
3. Santana, Stephanie MPH; Brach, Cindy MPP; Harris, Linda PhD; Ochiai, Emmeline MPH; Blakey, Carter BS; Bevington, Frances MA; Kleinman, Dushanka DDS, MScD; Pronk, Nico PhD, MA, FASCM, FAWHP Updating Health Literacy for Healthy People 2030: Defining Its Importance for a New Decade in Public Health, Journal of Public Health Management and Practice: November/December 2021 - Volume 27 - Issue - p S258-S264 doi: 10.1097/PHH.0000000000001324
4. Cutilli, C. C., & Bennett, I. M. (2009). Understanding the Health Literacy of America results of the National Assessment of Adult Literacy. *Orthopaedic Nursing*, 28(1), 27–32. <https://doi.org/10.1097/01.NOR.0000345852.22122.d6>

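### Providers may learn the intervention arm before the consultation, and silence about controls does not stop them communicating differently with patients they know to be in an intervention arm

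*Combined protocol and SAP*

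**What the plan says.** The title and section 2 (Objectives) declare the design: "We propose a prospective randomized open label trial". Section 5 sets out the arms: "There will be three cohorts in total: the control group, the standardized AVI only group, and the standardized AVI with teach back group". On timing it says: "Patients will be randomized before the office visit".

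Two consecutive sentences in section 5 govern what providers know. The first is "Providers will be told which intervention group a patient is a part of". The second is "If a patient is in the control group the providers will not be informed as to not impact behavior". Neither says at what point between randomization and the end of the visit the provider is told.

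Three other statements bear on whether a provider could recognise a participant who carries no flag:

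- Section 10 (Consent Process): "Patients will be contacted with permission from their primary providers prior to their scheduled visit". Consent is normally by telephone with electronic signature; in-person consent 30 minutes before the appointment is the fallback.
- Section 5: "All patients included in the prospective study will complete an arthritis adapted REALM (REALM-A) form at the observed visit".
- Section 5 also keeps the providers who deliver the intervention off the research team.

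The primary outcome is a telephone score, taken 1 to 2 weeks later, of how far the patient's understanding matches what was covered at the visit.

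**The concern.** The plan recognises that knowing the arm can change how a provider behaves, and it guards against this for controls only. For both intervention arms the provider may walk into the room already knowing the assignment. The provider needs it only at the end, to write the AVI and run the teach-back.

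A provider who knows that a patient will be tested on recall under a new discharge process may explain more slowly, repeat more, or simplify the plan during the consultation. None of that is the AVI or the teach-back, but it acts directly on the recall score, and on satisfaction (a secondary outcome) by the same route. The comparison with control would then measure the assigned discharge process plus any extra consultation effort, with no way to separate them at analysis. The contrast between the two intervention arms is exposed as well, because the exact arm is disclosed. Section 5 expects randomization to spread confounders equally, but randomization cannot balance behaviour that arises after the assignment is revealed.

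**Working it through.** The documents give no sample size, allocation ratio, consent rate or effect size, so there is no figure to reproduce. The check is what the flag tells a provider, and when.

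**Step 1: flagged patients.** Section 5 tells the provider the specific intervention arm. For these patients the arm is known with probability 1, whatever the consent rate. If allocation is 1:1:1 (an assumption), this covers 2/3 of participants. If the control share is 1/4 to 1/2, it covers 3/4 to 1/2 of them. Silence about controls has no bearing on this group.

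**Step 2: timing.** Randomization precedes the visit. No sentence delays disclosure, and none standardizes the rest of the consultation. The text therefore permits early disclosure, although it does not state that it happens.

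**Step 3: unflagged patients.** An unflagged patient is never an intervention patient. Whether the provider can go further and infer control depends on what else the provider knows. Let *c* be the share of approached patients who enrol and *a* the control share of allocation. Among approached patients without a flag,

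P(control | no flag) = c·a / (c·a + 1 − c).

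For example, with a = 1/3 and c = 0.5: 0.1667 / (0.1667 + 0.5) = 0.25.

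| Assumed c | a = 1/4 | a = 1/3 | a = 1/2 |
|---|---|---|---|
| 0.3 | 0.10 | 0.13 | 0.18 |
| 0.5 | 0.20 | 0.25 | 0.33 |
| 0.7 | 0.37 | 0.44 | 0.54 |
| 0.9 | 0.69 | 0.75 | 0.82 |
| 1.0 | 1.00 | 1.00 | 1.00 |

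The formula leaves out patients who were never approached. If the provider cannot tell who was approached, the probabilities are lower still. If the provider knows that the patient enrolled, the probability is 1. So the protection for controls runs from substantial to none, depending on a fact that the documents do not settle.

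**Step 4: effect of delaying disclosure.** If no patient is flagged until discharge, the absence of a flag carries no information during the consultation. Even a provider who knows that a patient enrolled then has P(control) = a, which is 1/3 under equal allocation, instead of 1. At discharge the inference returns for any patient known to be enrolled, which is why cues to enrolment also matter.

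**The case against.** The strongest reply is that this is an open-label trial. No masking of providers is claimed. The sentence about controls states a purpose and does not assert that behaviour is unaffected. Providers write the AVI and conduct the teach-back, so they cannot be kept unaware at delivery. All of this stands. What it does not explain is why the assignment may be known before the consultation, when it is needed only at discharge.

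A reader might infer something stronger: that controls are in effect unmasked, because any participant without a flag must be a control. The documents do not support that. The step needs a provider who knows that the patient enrolled, and this is never stated. Permission to contact a patient is not notice of consent, and the primary provider need not be the treating rheumatologist. Consent is mainly by telephone, a coordinator assists with it, and nothing places the provider in the room for it or for the REALM-A. At assumed consent rates of 50% to 70% with equal allocation, an approached patient without a flag is a control only 25% to 44% of the time. Silence may therefore do some good. Equally, nothing in the plan keeps enrolment hidden, so its protection is not assured.

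It is also fair to say that the absence of a timing rule is silence and not proof of early disclosure. The point is that the plan should settle the timing.

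**Conclusion.** The concern holds in this form: the plan lets providers be told the intervention arm at any time after pre-visit randomization, and its one safeguard does not reach the patients whose arm is disclosed. Different communication with those patients during the consultation could raise recall and be attributed to the AVI or teach-back. For controls, the safeguard works only as far as providers are unaware of who enrolled.

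The first conclusion follows from section 5 alone. The two-thirds figure rests on assumed equal allocation, and the probabilities for unflagged patients rest on assumed allocation and consent rates. The size of any bias in the recall score cannot be computed from the documents. It would be wrong to conclude that the plan makes a masking claim that it breaks. The change is worth making because it is cheap and because the bias cannot be removed once visits have taken place.

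**What to change.** In section 5, state that the provider receives an intervention patient's assignment only at the discharge step, after the consultation and once the plan has been agreed, for example by sealed card or a message in the electronic record.

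Continue not to notify providers about controls. A card for every participant, including one for usual discharge, would look tidier but should not be used. It would identify every control to a provider trained in the AVI and teach-back, immediately before the step under test, and so give up the protection that silence may offer.

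In sections 5 and 10, have the coordinator complete consent and the REALM-A out of the provider's sight, so that enrolment of an unflagged patient is not signalled.

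Report the provider awareness that remains at discharge as a limitation of the open-label design. A limitation statement alone, without the change in timing, would not reduce the bias.

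The cost is a wording change and a brief hand-over, with no extra staff or patients. The AVI is started slightly later. Since section 3 (Background) plans to assess feasibility in terms of time, the hand-over should be noted in that assessment.

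### For returning patients the pooled retention score may partly reflect knowledge held before the visit; randomisation should be stratified, and the primary result presented, by new versus follow-up visit

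*Combined protocol and SAP*

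**What the plan says.** Section 2 (Objectives) defines the endpoint: "Primary outcome will be level of retention based on the Follow-up Telephone Protocol". Section 5 (Procedures Involved) gives its content: "patients will be asked specific questions pertaining to their visit in terms of diagnosis, medications, plan, and follow-up appointments". The scoring standard is agreement with the visit: "We will score whether their understanding of their disease and management corresponds with what was discussed at the prior visit". The text gives no item count, weights or range, and the telephone script itself is not part of the supplied text.

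Section 4 sets eligibility by age and by "Patients seen in the RUMCRC", and excludes telemedicine visits and patients whose primary language is not English. It does not require a new diagnosis, a changed regimen or a new instruction. The call is timed from the visit: "Within 1-2 weeks after the patient's initial visit, a standardized phone call will be performed". Taken alone, the word initial in that sentence might suggest first visits only. But the baseline list in section 5 includes "new patients versus follow-up visit", so returning patients are enrolled.

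Teach-back, used in one of the two intervention arms, has the patient "repeating to the provider which changes, and future management had been agreed upon during the visit". Patients are randomised before the visit, and section 5 relies on randomisation to balance confounders. The method of randomisation is not described, and no stratification is mentioned. Section 6 (Data Management) describes summary tables and, where appropriate, 95% confidence intervals. It gives no model, adjustment or subgroup.

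**The concern.** The score asks whether the patient's account matches what was discussed. It does not ask whether the patient learned it at that visit. A new patient may have to acquire all four domains. A returning patient with an unchanged diagnosis and regimen may already hold two of them and would get full credit in any arm. Because knowledge before the visit is not measured, the score cannot separate retention from this visit from what was known already. Teach-back, as described, rehearses changes and future management, which is narrower than the score.

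Two consequences are possible. First, items that patients in every arm answer correctly add nothing to the difference between arms, so the raw difference understates the effect on content that was new at the visit. A small or null result would then be hard to interpret. Second, visit type is plausibly prognostic for the score, so a chance imbalance in the new-to-returning mix would move the arm means for reasons unrelated to the intervention.

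**Working it through.** The plan gives no sample size, effect size, SD or visit mix, so it has no figure to reproduce. Everything below is illustrative and rests on the stated assumptions.

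**1. Raw mean difference.** Let f be the share of patients who are returning with diagnosis and medications unchanged, and k the share of the score that is carried over and equal across arms. The fraction of the effect retained is 1 - f × k.

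- k = 0.5 (two of four equally weighted domains), f = 0.5: 1 - 0.25 = 0.75
- k = 0.5, f = 0.6: 1 - 0.30 = 0.70
- k = 0.5, f = 0.8: 1 - 0.40 = 0.60
- k = 0.25, f = 0.5: 1 - 0.125 = 0.875

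If written instructions also refresh old knowledge, the shrinkage is smaller.

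**2. Power, when the carried-over items still vary between patients.** Assume four domains, each with SD 1, correlation rho between domains, and an effect of 0.4 on each responsive domain. Diagnosis and medications are unresponsive in a returning share r. The test is two-sided at 0.05 with 80% power, comparing two arms 1:1.

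- Effect on the four-domain sum: Δ = (1 - r) × 1.6 + r × 0.8. At r = 0.7, Δ = 0.48 + 0.56 = 1.04, which is 65% of 1.6.
- Variance of the four-domain sum: 4 + 12 × rho.
- Plan plus follow-up only: effect 0.8, variance 2 + 2 × rho.
- n per arm = 2 × (1.960 + 0.842)² × variance / effect², rounded up.

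**3. Power, when the carried-over items are at ceiling.** Now give diagnosis and medications no variance in returning patients, and compare arms within visit type. The average variance is (1 - r)(4 + 12 × rho) + r(2 + 2 × rho), with the same Δ. At r = 0.7 and rho = 0.3 this is 0.3 × 7.6 + 0.7 × 2.6 = 4.1, so n = 15.70 × 4.1 / 1.04² = 59.5, or 60.

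Patients per arm at r = 0.7:

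| rho | Four domains, carried-over items vary | Four domains, carried-over items at ceiling, compared within visit type | Plan + follow-up only |
|---|---|---|---|
| 0 | 59 | 38 | 50 |
| 0.3 | 111 | 60 | 64 |
| 0.5 | 146 | 75 | 74 |

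At the n that gives plan plus follow-up 80% power, the four-domain score in the second column has 74%, 57% and 52% power for rho 0, 0.3 and 0.5. In the third column the loss disappears or is trivial. Even when the items vary, the direction is not universal: at rho = 0 and r = 0.5 the four-domain score needs 44 per arm against 50.

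**4. Chance imbalance.** If the mean score differs by g between returning and new patients, and the returning share differs by Δp between two arms, the unadjusted difference moves by Δp × g. The documents give neither quantity. Randomisation makes the expected Δp zero, so this is random error. Stratifying keeps Δp close to zero, and including the stratum in the comparison removes the Δp × g shift and the between-visit-type variance.

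**The case against.** The strongest reply is that the score measures what the trial set out to measure. Section 2 speaks of retention of disease management, section 5 scores understanding of disease and management, and knowing one's current diagnosis and drugs belongs to that. Written instructions are customised with no stated limit to changes, so the narrower target applies only to teach-back. The questions are tied to the visit, and the unseen script may already ask about medication changes. These points stand, and they are why the four-domain score should remain primary.

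A reader might infer that returning patients already knew their diagnosis and medications, that their score is therefore largely old knowledge, and that any effect is diluted. The documents do not support this. They contain no data on prior knowledge, and the background in section 3 on low health literacy argues against assuming it. Plan and follow-up are specific to the visit, medications can change, and even the largest k used above is half the score. New patients and visit-specific items still carry effect. Nor does a smaller raw difference by itself mean lost power, as step 3 shows.

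A reader might also want the primary score limited to items new or changed at the visit. That changes the research question. It also carries a risk: only intervention-arm providers are told the allocation, and they write the structured instructions, so which items count could depend on arm. Dilution could then become bias.

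Finally, chance imbalance affects any prognostic factor. That is true, but this factor is plausibly tied to the score and already collected.

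**Conclusion.** The point holds in limited form. The documents establish that one score pools four domains across new and returning patients, that knowledge before the visit is not measured, and that no use of visit type in randomisation, scoring or analysis is described. It follows that carried-over knowledge can enter the score and may shrink the raw difference between arms. With two equally weighted domains carried over, 60% to 75% of the effect would remain for f between 0.8 and 0.5; with one carried over and f = 0.5, 88%. These figures assume equal weights and no effect of the intervention on carried-over items. The true size cannot be determined from the documents. Power may fall materially if the carried-over items vary between patients, and little or not at all if they are at ceiling and arms are compared within visit type. The issue is sensitivity and chance imbalance; it does not bias the comparison between arms.

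**What to change.** 1. Stratify the pre-visit randomisation by new versus follow-up visit, which should normally be known at scheduling.
2. State a between-arm comparison of the primary score that includes this stratum, and present the primary result by stratum.
3. Keep the four-domain score as primary. Report two domain scores as secondary: diagnosis and medications, and plan and follow-up.
4. If a score for items new or changed at the visit is wanted, make it secondary only. Classify items from the same visit-note source in every arm, by someone blind to allocation, so that more detailed instructions do not change which items count.

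The cost is a short amendment, one binary randomisation factor and slightly more analysis, using a variable already on the baseline list. No extra patients or visits are needed. Estimates within each stratum will be less precise than the overall result and should be read that way.

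### The primary retention score is a study-team judgment, and the supplied text neither keeps the scorer from knowing the arm nor names one reference record for all three arms

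*Combined protocol and SAP*

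**What the plan says.** The title (section 1) describes "A Prospective Randomized Open Label Trial". Section 2 (Objectives) states: "Primary outcome will be level of retention based on the Follow-up Telephone Protocol". That instrument is named, but its content is not in the supplied text.

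Section 5 (Procedures Involved) adds that all groups receive a standardized call 1 to 2 weeks after the visit, with specific questions on diagnosis, medications, plan and follow-up appointments. It gives the scoring in one sentence: "We will score whether their understanding of their disease and management corresponds with what was discussed at the prior visit".

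On knowledge of the allocation, section 5 says: "Patients will not be told which group they are in unless they explicitly ask". Providers are told the group for intervention patients and are not informed for controls. It also says: "No providers that are implementing the intervention will be a part of the research team".

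On visit records, providers in the two AVI arms use a template to write "customized after visit instructions for the patient that will be in addition to the after-visit summary", and their training covers "accessing standardized AVI templates on EMR". Controls have the clinic's current discharge process. Section 3 (Background) reports from a retrospective study at this clinic that "written AVI were an underutilized resource".

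**The concern.** Two gaps bear on the same number. First, section 5 deals with what patients and providers know of the allocation but not with what the person producing the primary score knows. A scorer who knows the arm may credit partial answers about the plan or the disease more readily in one arm than in another.

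Second, the score measures agreement with a reference, and the reference is not identified. If the AVI text serves as the reference where it exists and something else serves where it does not, two things follow. The standard differs by arm, and the presence of the AVI tells the scorer which arm is being scored.

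The direction of the second effect is not predictable. Patients scored against a sheet they took home may score higher. A fuller reference may also contain more items to miss, which lowers the score. Both problems arise after allocation, so randomization does not protect against them.

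**Working it through.** The documents give no figure to reproduce, so the check sets the relevant statements side by side.

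**1. Who is kept from knowing the arm?**
- Patients: in part; they are not told unless they ask (section 5).
- Providers: told for intervention patients, not told for controls (section 5).
- Caller and scorer: no statement in any section.

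**2. Do other rules mask the scorer indirectly?**
- Section 6 (Data Management) codes data stored for analysis, requires a key to interpret them and limits access to persons approved through the IRB. Section 9 (Confidentiality) limits access to those directly involved in obtaining data. These rules protect confidentiality. A caller or scorer is someone who obtains data, so the rules as written do not keep that person from the allocation.
- Section 5 keeps implementing providers off the research team. This separates delivery from assessment but does not hide the arm from the team.
- The patient survey in section 5 asks how after visit instructions were implemented, and AVI templates sit in the EMR. Either could reveal the arm to a scorer who sees it. No section says the scorer will see them, and none says the scorer will not.

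**3. Which record establishes what was discussed?**
- AVI-only arm: customized AVI in addition to the after-visit summary.
- AVI with teach-back arm: the same written material, plus the spoken teach-back.
- Control arm: the current standard process. Written AVI there are underused, which does not mean absent.
- Named as the scoring reference: none of these, and no visit note or provider report.

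**4. Which comparisons are exposed?** A reference that differs by arm affects mainly the comparisons with control, because both intervention arms receive the written AVI. A scorer's knowledge of the arm could affect all three pairwise comparisons.

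**5. One line of illustration, every input assumed.** With no true effect, a scoring shift of 0.25 SD in one arm and a two-sided 5% t-test (noncentral t, df = 2n − 2, noncentrality 0.25 × √(n/2) = 0.97, 1.25 and 1.77), the false-positive rate would be 15.9%, 23.6% and 42.1% at 30, 50 and 100 per arm; over shifts of 0.1 to 0.5 SD and these sizes it runs from 6.7% to 94.0%.

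**The case against.** The strongest objection is that the plan bases the primary outcome on a named instrument that was not supplied. A scoring key and reference source would naturally sit there, and it could also assign the caller. That stands, and it makes the reference half of this point conditional: neither item is in the supplied text, and the Follow-up Telephone Protocol should be checked.

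The plan also has real safeguards. The call is standardized and made to all groups. Diagnosis, medications and appointments are largely checkable facts, and implementing providers are outside the team. These narrow the room for judgment. They leave room where an answer about the plan or the disease is partly right, and they do not fix the reference.

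The remedy has a weakness too. A key that does not depend on the AVI may leave out the fullest record of the agreed plan in two arms, and patients may mention handouts or teach-back on the call. Both are accepted costs of a reference that is the same kind of record in every arm.

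Three stronger readings are tempting. A reader might infer that the plan provides for arm-aware scoring, or that the AVI will be the reference. The text says neither; it only fails to prohibit the first and to settle the second. A reader might take the illustrated rates as the size of the bias. They show what an assumed shift would do, under a test the plan does not specify, and they model lenient scoring, not a reference that differs by arm. A reader might also infer from the deletion of data in section 6 that masked rescoring is ruled out. Deletion comes only at completion, so it does not prevent rescoring before then.

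**Conclusion.** The point holds as a risk of bias in the sole primary outcome. On the supplied text, the scorer is not prevented from knowing the arm, and no single reference record is named for all three arms. The documents do not show that arm-aware scoring will take place or that any shift exists.

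The size cannot be determined from the documents. The illustrated range is too wide to rank the problem and carries no weight in this conclusion. The case for acting is that the affected score is the only primary outcome, it rests partly on judgment, and the remedy is cheap. It should be fixed, with medium confidence, because the unseen Follow-up Telephone Protocol may already settle part of it.

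**What to change.** Amend section 5 as follows.

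1. **Masked scoring.** An existing team member without access to the allocation, the AVI text or the survey items about AVI scores the answers. REDCap, already in use (section 8), can hold the access restriction through user rights. If the caller cannot be masked, the caller records answers verbatim, item by item, and the masked member scores them. Any unmasking is recorded.
2. **One reference for all arms.** Before the call, a team member other than the scorer fixes an answer key covering diagnosis, medications, plan and follow-up. The key is drawn by one written rule from one record type that exists in all three arms, so that it does not depend on whether an AVI was written. The sponsor should name that record; the documents do not say outright that controls receive the after-visit summary. The number of key items is reported by arm as a check.

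If the Follow-up Telephone Protocol already fixes either item, say so in section 5. If roles cannot be split (team size is not stated), apply item 2 alone. That reduces the dependence of the reference on arm but does not mask the scorer.

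The cost is protocol wording, a permission setting, a split of roles and a short abstraction per patient. Two weaknesses remain. Some unmasking will occur when patients mention handouts or teach-back. The source record may also still differ somewhat by arm, because providers know which of their patients are assigned to an intervention.
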